11 APPENDICES

11.1 APPENDIX 1: DATA DERIVATION DETAILS

A1.1 Definition and use of visit windows in reporting

Time points for follow-up visits are not determined by the study protocol. It is only suggested to perform those every 8 to 12 weeks. In order to be able to perform statistical analyses, documented visits will be transferred into corresponding time windows.

The definition of single time windows can be taken from the following table:

	Treatment Phase 1	Treatment Phase 2	Treatment Phase 3	Treatment Phase 4	Treatment Phase 5	Treatment Phase 6
Weeks after Baseline	0 to 15	16 to 25	26 to 35	36 to 45	46 to 55	56 to 65
	Treatment Phase 7	Treatment Phase 8	Treatment Phase 9	Treatment Phase 10	Treatment Phase 11	and so on
Weeks after Baseline	66 to 75	76 to 85	86 to 95	96 to 105	106 to 115	
	Survival 1	Survival 2	Survival 3	Survival 4	Survival 5	and so on
Months after discontinuation	0 to 15	16 to 21	22 to 27	28 to 33	34 to 39	

In case more than one visit was performed within one time window, than the later one

In case more than one visit was performed within one time window, than the later one will be used for analyses "by time windows" with the following exceptions:

- Adverse events will be analyzed from all documented visits.
- Duration of PFS will be determined using the first occurrence of a progression of disease.

The study phase while patients are treated with Torisel[®]/Sutent[®] is defined as follow-up phase. The follow-up of subjects after discontinuation of Torisel[®]/Sutent[®] is defined as survival phase.

A1.2 Definition of Analysis Populations/Sets

Not applicable.

A1.3 Further Definition of Endpoints

Demography

```
Age (years) = (date of baseline visit – date of birth + 1)/365.25

BMI = body weight (kg) / body height (m)**2
```

Oncological history

For computation of duration of RCC, MCL and GIST and time since first confirmed metastasis (not for MCL) an arbitrary day 1 will be added and thereafter the SAS function for computing with date values will be used.

```
Duration of RCC/MCL/GIST (months) = (1/month/year \text{ of start of } Torisel@/Sutent@/Inlyta@ treatment } - 1/month/year of date of histological confirmation of RCC/MCL/GIST)*12/365.25
```

First metastases (months) = (1/month/year of baseline visit - 1/month/year of date of first confirmation of metastasis)*12/365.25

Survival

In case an event (either death or progression) was present and date of event was documented, the following definitions was used:

Overall Survival (OS, months) = $\frac{\text{date of death} - \text{date of baseline visit} +1}{365.25 *12}$

Progression Free Survival (PFS, months) = (minimum of (date of death, date of progression) – date of baseline visit + 1)/365.25 * 12.

In case information on dates were partly or completely missing or contradictory, the following was done:

• PFS:

- o the presence of a progression was confirmed, but no date was documented: if date of last intake of study medication was given, this date was used as date of progression, otherwise the date of the last visit with a documented "non-progression (e.g. SD)" was used as date of progression.
- o the presence of a progression was confirmed, but dates within a visit and on final documentation were contradictory, the prior date was used.
- o in case a death was documented within a survival follow-up/ within sequence 2 for subjects from sequence 1, but no progression was documented within regular study, the date of last visit + 1 day was used as date of progression.
- o in case no progression was documented, subject was censored with the latest available contact date / assessment date within study/within sequence.
- o in case these rules led to a missing duration or a negative duration, duration was set to "1 day".

• OS:

- o in case a death was documented, but date of death was unknown, the date of death was substituted with the latest available date for the patient (last visit, last contact date, date of assessment)
- o in case no death was documented, subject was censored with the latest available contact date / assessment date within study.
- o in case these rules led to a missing duration or a negative duration, duration was set to maximum of (PFS,"1 day").

Response to therapy (Recist criteria/ Cheson criteria)

Response to therapy according to the Recist/ Cheson criteria will be analyzed using the physician's assessment as documented in the CRF. As neither "size of lesion", "new lesions" or "increase in size" are defined as key fields, contradictory answers will not overvote physicians assessment.

"Best response" will be analyzed using the physician's assessment at final visit. If "Best response" is missing it will be determined from the best response documented during previous follow-up visits.

Treatment

Treatment duration (weeks) = (date of death or date of drop-out or date of end of treatment with Torisel®/ Sutent® - date of first infusion within the registry + 1)/365.25 * 52.

Therapy line

for patients with mRCC:

- Splitted therapy (due to coding) was only counted as one therapy line.
- All medication with an identical start date was counted as one therapy line.
- Interferons, interleukins and immunochemotherapies were summarized as "cytokines".
- Ongoing treatment with the medication documented was not counted as line.
- Bisphosphonates and other supplementary treatment will not be considered. for patients with MCL:
 - Splitted therapy (due to coding) was only counted as one therapy line.
 - All medication with an identical start date was counted as one therapy line.
 - Rituximab maintenance therapy and stem cell transplantation, both connected with previous immunochemotherapy (ATC L01 Antineoplastic agents and L03 Immunostimulants), were not counted as line.

Rituximub were counted as maintenance therapy, if

- physician's comment contained free text / phrases like "Erhaltung", "Erhalt", "Maintenance" or
- (last therapy prior to Rituximab resulted in remission (CR, PR or MR) and
- Rituximab was started directly after the last therapy (at most one therapy free month was tolerable).)

FKSI-15

For calculation of the FKSI-15 score documented values for questions 1-6, 8,9, 11, 12 and 14 will be reversed by subtracting the documented value from 4. All original scores (for questions 7, 10, 13 and 15) and all reversed scores will be summed, multiplied by 15 and devided by the number of answered questions resulting in a score within a range from 0 to 60. The FKSI-15 score cannot be determined if more than 7 questions are not answered.

FKSI-DRS score will be calculated like the FKSI-15 score considering only questions 1, 3, 4, 5, 6, 8, 11, 12 and 14 (multiply by 9). FKSI-DRS cannot be determined if more than 4 questions are not answered.

The 4 domains of FKSI-15 will be calculated like the FKSI-15 score. The following tables shows domains and related questions, multiplyer and maximal number of unanswered questions in order to give a valid score.

Domain	Questions	Multiplyer	Maximal number of unanswered questions
Signs and symptoms	1, 2, 3, 4, 5, 6, 12, 13	8	4
Respiratory symptoms	8, 11	2	1
Quality of life	7, 10, 13, 15	4	2
Emotional symptom	9	1	0

EQ-5D (TTO)

EQ-5D-TTO will be calculated from EQ-5D raw values according to the following formula (Greiner, W. et al. 2005):

EQ-5D-TTO = 0.999

- 0.099 * (1*Subject has some problems with walking around + 2 * Subject cannot walk around)

- 0.087 * (1*Subject has some problems with self-care + 2 * Subject has extreme problems with self-care)

- 0.112 * (1*Subject states moderate pain or discomfort + 2 * Subject has extreme pain or discomfort)

- 0.129 * (Subject cannot walk around)

- 0.091 * (Subject has extreme pain or discomfort)

- 0.065 * (Subject is extremely anxious or depressive)

- 0.323 * (Subject states major problems in at least one dimension).

EQ-5D-TTO-values range from -0.205 to 0.999.

Laboratory values

Additional queries were written in the following cases:

- calcium > 10 mmol/L
- albumin > 100 g/L
- hemoglobin > 20 g/dL
- LDH < 80 U/L or > 1000 U/L
- albumin in % of total protein.

Laboratory values were set to "missing" if the documented values were outside the ranges given in the following table:

Laboratory parameter	Lower plausibility range	Upper plausibility range
Neutrophils	6%	100%
Lymphocytes	2.5%	85%
Monocytes	-	26%
Eosinophils	-	16%
Basophils	-	5%
Leukocytes	-	28 G/L
Platelets	-	1000 G/L
Hemoglobin*	-	20 g/dL
Creatinine	-	12 mg/dL
Calcium*	-	10 mmol/L
Sodium	-	320 mmol/L
Potassium	-	15 mmol/L
Phosphate	-	4 mmol/L
Magnesium	-	7 mmol/L
ALT (GPT)	1 U/L	1400 U/L

Laboratory parameter	Lower plausibility range	Upper plausibility range
AST (GOT)	1 U/L	1400 U/L
Gamma-GT	1 U/L	1400 U/L
Alkaline Phosphatase	1 U/L	5100 U/L
Total bilirubin	-	25 mg/dL
Albumin	-	100 g/L
LDH*	80 U/L	1000 U/L
Cholesterol	-	26 mmol/L
Triglycerides	-	35 mmol/L
HbA1c	1%	10%
Glucose	-	_**
TSH	-	21 mU/L
beta-2 Microglobulin	-	-

^{*:} Risk factors according to Motzer score will be set prior to check on plausibility.

CYP3A4-inducing and inhibiting substances

A combination of Torisel® and CYP3A4 influencing substances should be handled carefully. Thus documented concomitant medication will be checked manually for CYP3A4 inducing and inhibiting substances by the medical expert.

If the number of patients who received either CYP3A4 inducing or inhibiting substances is sufficiently large, parts of the safety analysis will be repeated for those subgroups.

Comorbidities

In order to analyze data from prior and current version of the CRF regarding comorbidity, the categories presented in the current versions will be MedDRA coded. As the terms "Chron. Magen-Darm-Erkrankungen" and "Andere Krebserkrankung (maligne)" do not have an equivalent, those will be translated to "Chronic gastrointestinal disease" and to "Other malignant neoplasms". A footnote will be added to state that coding is not completely according to MedDRA.

^{**:} No plausibility range defined as values do not need to be fasting glucose values.

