In total, the treatment of approximately 100 patients per year and product should be documented. This number of patients was chosen to capture a broad range of medical prescription habits and assess the target criteria as significantly as possible. The probability of occurrence of at least one "uncommon" (>1/1000, <1/100) AE is between 0.33 and 0.98 and for a "rare" AE (>1/10,000,<1/1000), between 0.04 and 0.33.

The planned number of 200 sites to be included according to Amendment III allows a representative cross-section across German oncology practices or clinics.

With Amendment VI, the efficacy of axitinib regarding the progression-free survival and overall survival is to be evaluated in the 3rd (and 4th) line of therapy and a correlation with patients on axitinib in the 2nd line of therapy is to be performed.

Patients already documented in STAR-TOR (n = 92; status of 06/30/2017) who received axitinib in the 2nd line of therapy, i.e. with a treatment course of sunitinib-axitinib, will be used as a (historical) comparison group for the comparison with the 3rd and 4th line of therapy, particularly because patients with axitinib in the 2nd therapy line are only rarely expected after the guideline amendments and therefore cannot be newly enrolled.

Patients already documented in STAR-TOR with axitinib in the 3rd line of therapy or 4th line of therapy should not be used to answer the expanded question (see above) as none of these patients received nivolumab or another active substance newly approved in 2016 in the 2nd line of therapy, but received other therapeutic options. It cannot be excluded that the deviating pretreatment/treatment course will impact the efficacy of axitinib in the subsequent lines of therapy as compared with current therapy guidelines.

[figure not shown]
Approximately 45 patients with a PFS event should be documented in the 3rd line with axitinib after the previous therapy sequence, e.g. sunitinib - nivolumab. Therefore, mPFS and mOS can be estimated with sufficient precision (see Statistical Analysis Plan). In order to recruit 45 new third-line axitinib patients after e.g. sunitinib-nivolumab pretreatment in STAR-TOR, approximately 45 months will be required (assuming the usual therapy periods).

Assuming that the last patient is enrolled after 45 months and a progression event (or death) occurs after approximately 6 months, a runtime of approximately 4 years should be assumed after implementation of Amendment VI.

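### A confirmed progression with neither a progression date nor a last-intake date is dated to the last visit recorded as progression-free, shortening PFS in those patients by up to one visit interval

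*SAP*

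**What the plan says.** The PFS rules are in SAP section 11.1, Appendix 1, A1.3, under Survival.

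- **Formula.** "Progression Free Survival (PFS, months) = (minimum of (date of death, date of progression", counted from the baseline visit plus one day and expressed in months.
- **Undated progression, first choice.** The rule applies when "the presence of a progression was confirmed, but no date was documented: if date of last intake of study medication was given"; the last-intake date then becomes the progression date.
- **Undated progression, fallback.** "otherwise the date of the last visit with a documented 'non-progression (e.g. SD)' was used as date of progression".
- **Death in follow-up or in sequence 2 with no progression documented.** "the date of last visit + 1 day was used as date of progression".
- **Default.** A missing or negative duration is set to 1 day.

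A1.1 states that "Duration of PFS will be determined using the first occurrence of a progression of disease". It also says that visit times are not fixed by the protocol: "It is only suggested to perform those every 8 to 12 weeks".

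The SAP plans no sensitivity analysis for imputed progression dates, and none of the effectiveness tables in its section 9 counts them.

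**The concern.** A visit documented as stable disease is evidence that progression had not yet occurred. Placing the event on that date contradicts the source record and does not fit the A1.1 principle of timing PFS by the first occurrence of progression. It also sits oddly beside the neighbouring rules. A death without documented progression is placed one day after the last visit, and an undated death goes to the latest available date. Only the undated progression is moved back to a date on which the event is known not to have happened.

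PFS is a listed effectiveness outcome. Its Kaplan-Meier quartiles are reported for each drug and indication, and the mRCC tables compare it by line, age, LDH and histology with log-rank tests. Protocol section 11 also plans a comparison of the three drugs. Events timed on a different footing enter all of these, and the reader cannot see how many there are.

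**Working it through.** The plan gives no figure that depends on this rule, so there is nothing to reproduce first. The check sizes the effect.

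**Inputs**
- Visit interval: 8 to 12 weeks, suggested only (SAP A1.1).
- PFS time scale: exponential with a median of 6 months. This is an assumption, with 4 and 10 months as the range. The only related figure is in the case number estimate of protocol section 11: "a progression event (or death) occurs after approximately 6 months". It concerns third-line axitinib.
- Share of progressions reaching the fallback: not given. Values of 5% to 50% are tried.

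**Step 1: where the event falls.** Let L be the last progression-free visit, D the visit that found progression and T the true time, so L < T ≤ D. The fallback sets the event at L. The loss is D − L against the detecting visit and T − L against the truth. Neither can be negative, so the fallback can only shorten PFS.

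**Step 2: loss against the detecting visit.** This is one interval, weeks × 7 / (365.25/12):
- 8 weeks: 56 / 30.44 = 1.84 months
- 12 weeks: 84 / 30.44 = 2.76 months

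It is longer if visits were missed or spaced more widely.

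**Step 3: mean loss against the true date.** For an exponential time with rate λ = ln 2 / 6 = 0.1155 per month and interval Δ, the mean of T − L is 1/λ − Δ/(e^(λΔ) − 1):
- Δ = 1.84: 8.66 − 7.77 = 0.89 months
- Δ = 2.76: 8.66 − 7.35 = 1.31 months

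This is a little under half an interval (0.92 and 1.38). Simulated medians of 4 to 10 months give 0.87 to 1.34 months.

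**Step 4: effect on the group median.** Simulation without censoring, visits randomly 8 to 12 weeks apart, 6-month true median, unaffected patients dated at the detecting visit:

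| Share affected | Median PFS (months) | Fall |
|---|---|---|
| 0% | 7.14 | – |
| 5% | 7.08 | 0.06 |
| 10% | 7.03 | 0.11 |
| 20% | 6.92 | 0.22 |
| 50% | 6.49 | 0.65 |

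A separate run of the same kind gave 7.08 at 0% and 6.73 at 30%, a fall of 0.35. With a 4-month median the fall is 0.10 at 10% and 0.50 at 50%; with a 10-month median it is 0.16 and 1.44.

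**Step 5: no earlier progression-free visit.** The flow charts in both documents show tumor or response assessment at follow-up visits but not at enrollment. An undated progression found at the first follow-up may therefore have no documented progression-free visit before it. The duration is then missing and the default sets it to 1 day. With a 6-month median, the share of progressions before the first follow-up is 1 − 2^(−Δ/6): 19% at 8 weeks and 27% at 12 weeks. Only those that also lack both dates are affected.

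**The case against.** The strongest reply is that the fallback is a second-tier rule. It needs two dates to be missing after edit checks and queries, and the end-of-treatment date is an expected item because treatment duration is computed from it. The affected share may be very small. The evaluation is descriptive, with no hypotheses or decision rules, so no power or type I error is at stake. The A1.1 sentence on first occurrence was written for choosing among several visits in one window, not for imputing dates. All of this stands and limits the weight of the point. It does not make the imputed date defensible.

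Several stronger readings are tempting but not supported:

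- **Every affected patient truly loses a full interval.** That holds only against the detecting visit. Against the true date it is about half.
- **Reported PFS is too short overall.** Dating at the detecting visit runs late (7.14 months against an assumed 6), and even at 50% affected the median of 6.49 stays above 6. The fallback lowers PFS relative to the other patients; a net downward bias against the truth is not shown.
- **The median drops by a whole interval at 30% affected.** This arises only if every patient is seen on the same rigid visit days. The plan fixes no such days, and with realistic spacing the fall is about 0.35 months.
- **The loss is 31% to 46% of expected PFS.** The 6-month figure belongs to third-line axitinib under the Amendment VI question, which was dropped; those sequences are now only listed.
- **The date of the form recording progression is ignored.** The CRF is not shown, and the rule on contradictory dates refers to dates within a visit and on the final form. A progression recorded at a dated visit may already count as dated. The SAP is unclear on this.
- **The last-intake rule also biases PFS downward.** It can err either way: early if treatment stopped for intolerance before progression, late if it continued past progression.
- **The share differs between drugs or lines.** Possible, but nothing in the documents shows it.

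**Conclusion.** The fallback is wrong as written. It assigns the progression to a date on which the patient was documented as not progressed, and nothing elsewhere in the plan corrects it. For an affected patient, PFS is shortened by up to 1.8 to 2.8 months against the visit that found progression, if visits keep to 8 to 12 weeks, and by 0.9 to 1.3 months on average against the true date. The effect on median PFS is about 0.1 month at 10% affected and becomes noticeable only if a large share is affected (0.35 at 30%, 0.65 at 50%). The average loss and the median figures rest on the assumed 6-month exponential median; the median figures also assume no censoring. The affected share is unknown. This is a point of coherence and transparency with a cheap remedy, not evidence that the registry's PFS results are materially distorted.

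**What to change.** Replace the first PFS bullet in A1.3 with this order for a confirmed but undated progression:

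1. The date of the first dated visit or final form that records progression. State explicitly that such a form date is used.
2. If there is none, the date of last intake, but only where the documented reason for stopping is progression.
3. Otherwise, the midpoint between the last progression-free visit and the next dated contact.

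Report the number of PFS events with an imputed date by drug. That count alone would show whether the rule matters.

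The cost is a short change of SAP wording and slightly more programming, using visit and contact dates that the SAP already works with. The downside is that an event may be dated up to one interval late under option 1, as happens to any progression dated at the visit that found it.

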1 AMENDMENTS FROM PREVIOUS VERSION(S)

Amendment from version 1.0

In the course of the NIS for patients with metastasized renal cell carcinoma treated with Torisel[®], regarded treatment and regarded indication was extended. In the NIS are currently included patients with metastasized renal cell carcinoma treated with either Torisel[®] or Sutent[®], patients with mantle cell lymphoma treated with Torisel[®] and patients with gastrointestinal stroma tumors treated with Sutent[®].

For this reason the statistical analysis plan had to be amended from version 1.0.

Amendment from version 2.0

In the course of the NIS for patients with metastasized renal cell carcinoma treated with Torisel[®], was further extended regarding treatment. Patients suffering from metastasized renal cell carcinoma being treated with Inlyta[®] are now also included in the NIS. Furthermore the documentation of two patient questionnaires (Functional Assessment of Cancer Therapy - Kidney Index - 15 (FKSI-15) and EuroQoL-5D (EQ-5D)) was added

for patients suffering from metastasized renal cell carcinoma.

Also the importance of the sequence of systemic treatments was strengthened leading to

Also the importance of the sequence of systemic treatments was strengthened leading to a new version of the case report form.

For these reasons the statistical analysis plan had to be amended from version 2.0.

Amendment from version 3.0

In the course of the NIS, the flow chart had to be updated as a starting visit for the 2nd therapy for mRCC patients was included.

Amendment in version 6.0

In the course of the NIS the following changes were implemented:

Rules for determination of therapy lines were added.

Additional plausible ranges for laboratory values were defined and actions after detections of not plausible ranges were defined.

Due to the possibility of documentation of treatment sequences, the determination of modified Motzer score was not possible without any doubt for the second treatment within a sequence. It was clarified, that modified Motzer score was determined only for 1st line patients.

The analysis on comorbidities was further specified, in order to combine data on comorbidities from old and new versions of the CRF.

Determination of time to progression and overall survival was further specified.

Amendment in version 7.0

In the course of the NIS, further specifications to determine therapy line for MCL subjects were added.

Amendment in version 7.1

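### SAP A1.3 gives three PFS outcomes for a late death without documented progression, and the only workable reading lets later survival set event status at the last visit

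*SAP*

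**What the plan says.** All the rules stand in SAP 11.1, Appendix 1, A1.3, under Survival.

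- **Formula.** Scope: "In case an event (either death or progression) was present and date of event was documented, the following definitions was used". Rule: "Progression Free Survival (PFS, months) = (minimum of (date of death, date of progression", less the baseline date, plus one day. A dated death without progression is an event on the death date.
- **List of exceptions.** Scope: "In case information on dates were partly or completely missing or contradictory, the following was done".
- **Third PFS rule in that list.** It applies when a death is found in survival follow-up, or in sequence 2 for a sequence 1 subject: "but no progression was documented within regular study, the date of last visit + 1 day was used as date of progression". It does not require the death date to be missing.
- **Fourth PFS rule.** "in case no progression was documented, subject was censored with the latest available contact date / assessment date within study/within sequence". It makes no exception for deaths.

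A1.1 adds only "Duration of PFS will be determined using the first occurrence of a progression of disease", which is silent on deaths without progression. The term for the regular study in the third rule has to be inferred from the A1.1 phases; the definition that begins "The study phase while patients are treated with Torisel" goes on to name Sutent but not Inlyta.

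PFS feeds Tables 2.3-1 and 2.3-2 and is repeated by treatment sequence (SAP section 5). Protocol section 11 lets documentation end through a change in therapy or intolerance. It places the first survival query 12 months after the final visit and later ones every 6 months.

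**The concern.** There are two linked problems.

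First, one patient meets the conditions of three rules with three different results, and neither A1.3, SAP 8.1.2 nor the table list in SAP section 9 says which governs. Two programmers could follow the text and report different medians.

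Second, settling the order does not finish the matter. If the third rule governs late deaths, two patients with the same last visit and no progression are treated differently because of what happens afterwards. The one who later dies has an event at that visit plus one day; the one still alive is censored. Kaplan-Meier estimation requires that status at a given time not be decided by later information. The PFS curve then partly reflects survival after the sequence and how well deaths are traced. For a descriptive registry the estimates are the product, so this matters even without a test.

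**Working it through.** The documents state no figure that depends on these rules, so there is none to reproduce.

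**1. One assumed patient.** Last visit day 183 with stable disease, last contact day 729, death day 730 in survival follow-up. Months = (days + 1)/365.25 × 12.

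| Rule | Calculation | Result |
|---|---|---|
| Formula | 731/365.25 × 12 | event at 24.0 |
| Third rule (progression on day 184) | 185/365.25 × 12 | event at 6.1 |
| Fourth rule, last assessment | 184/365.25 × 12 | censored at 6.0 |
| Fourth rule, last contact | 730/365.25 × 12 | censored at 24.0 |

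If the same patient were alive at last contact, only the fourth rule would apply. The event at 6.1 months exists only because of a death found about 18 months later.

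**2. Which order is intended.** If the formula or the fourth rule governed dated late deaths, the third rule would do almost nothing. Reading the third rule as an override that supplies a progression date to the minimum, and the fourth as meant for patients not known to have died, keeps every line in use. The version 6.0 entry in SAP section 1, "Determination of time to progression and overall survival was further specified", fits this.

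**3. Illustrative size.** All rates are assumptions:
- Exponential progression, median 10 months.
- A share of 10, 20 or 30% leaves without documented progression.
- The progression hazard after leaving is 1 or 50 times that before.
- Death follows progression by a median of 14 months.
- Enrolment is uniform from January 2008 to December 2020, with the cut in December 2021.
- Survival follow-up is complete, and survivors who left are censored at the last visit.

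There were 400,000 simulated patients per scenario. Medians in months:

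| Leave | Hazard | Third rule | Formula | Fourth rule, literal | True | Third rule − true |
|---|---|---|---|---|---|---|
| 10% | ×1 | 9.1 | 10.3 | 10.0 | 10.0 | −0.9 |
| 10% | ×50 | 9.1 | 10.1 | 10.0 | 9.0 | +0.1 |
| 20% | ×1 | 8.3 | 10.8 | 10.0 | 10.0 | −1.7 |
| 20% | ×50 | 8.2 | 10.2 | 10.0 | 8.1 | +0.1 |
| 30% | ×1 | 7.4 | 11.5 | 10.0 | 10.0 | −2.6 |
| 30% | ×50 | 7.2 | 10.3 | 10.0 | 7.1 | +0.1 |

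The third rule applies to about 8–9%, 16–17% and 24–26% of patients at 10, 20 and 30% leaving.

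**4. Incomplete survival follow-up.** With 20% leaving and 50% of patients lost to survival follow-up, the third rule reaches 8–9% of patients. Its median is about 0.9 months too low at ×1 (9.1 against 10.0) and about 0.9 too high at ×50 (9.0 against 8.1).

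**5. Drift in the same patients.** For patients enrolled 2008–2012 with 20% leaving, read in December 2013, 2016 and 2021, the third-rule median is 8.7, 8.2, 8.0 (×1) or 8.4, 8.1, 8.0 (×50). It falls as deaths accrue, without new tumour data; most of the fall comes before 2016.

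**6. Log-rank tests under the third rule.** Two groups of 150 with identical true PFS but 7 against 21 months from progression to death, 20% leaving, December 2021 cut: rejection at nominal 5% was 6.3% (×1) and 5.8% (×50). The effect at the final cut is small.

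**7. Two alternative analyses, 20% leaving.** Analysis (1) censors at the last tumour assessment and counts a death on its own date only if it falls within 12 weeks (the protocol's upper visit spacing, for illustration). Analysis (2) makes leaving without documented progression an event at the last visit for everyone.

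| Hazard after leaving | (1) | (2) | True |
|---|---|---|---|
| ×0.5 | 9.99 | 8.02 | 10.49 |
| ×1 | 9.96 | 7.98 | 9.99 |
| ×50 | 9.76 | 8.02 | 8.08 |

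At ×0.5 the true median lies outside the pair.

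**The case against.** The strongest reply is that the three-way conflict is a matter of wording: the third rule is narrower than the fourth, it supplies a date that the formula needs, and only one order makes sense. That stands, and the overlap can be cured by a stated precedence and an exception in the fourth rule. It does not answer the second problem, which arises under that intended order.

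The evaluation is also purely descriptive (Protocol section 11; SAP 4.1 and 4.2 give no hypotheses or decision rules). That stands and limits the consequence.

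A reader might infer more than the documents support:

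- **That reported PFS is biased downwards.** Steps 3 and 4 show that the direction depends on the leaving rate, the hazard after leaving and the loss to survival follow-up, none of which is given.
- **That the risk-group log-rank tests are invalid.** SAP 8.1.2 provides log-rank tests by risk group, but the mRCC PFS list in Table 2.3-2 names line, age, LDH and histology. Under the third rule the effect at the final cut is small.
- **That interim non-Pfizer tumour assessments are a major gap for sequence 1 PFS.** Protocol section 11 reports 17 patients in interim documentation at 15 September 2020, about 1% of the planned 1,600 (17/1,600).
- **That contact date versus assessment date changes the result much.** With 20% leaving, complete survival follow-up and the final cut, censoring survivors at last contact moves the third-rule median only from 8.27 to 8.40 (×1) or 8.17 to 8.23 (×50). It should still be settled.

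**Conclusion.** The point holds in this form. A dated late death without documented progression meets three rules with no stated precedence. Under the only reading that uses every line, later vital status decides event or censoring at the last visit. Tables 2.3-1 and 2.3-2 and the sequence analyses therefore depend on later survival and on the completeness of survival follow-up.

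That conclusion rests on the text alone. The size does not: across the hazards ×1 and ×50, the error ran from 2.6 months too low to 0.1 too high with complete survival follow-up (10–30% leaving), and from 0.9 too low to 0.9 too high with half lost (20% leaving). These ranges are not limits. The point should be fixed before the final analysis, but it does not threaten any decision.

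**What to change.** In A1.3:

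1. State that the third PFS rule takes precedence over the formula for these deaths, and add to the fourth rule the condition that no death was documented.
2. Censor survivors without progression at the last tumour assessment within the sequence, in place of the present choice between contact and assessment date.
3. Keep the present rule as primary, so that results stay comparable with earlier interim analyses and no late, data-aware change of primary rule is made.
4. Report, per product and line, how many patients the third rule applies to, and how many left without documented progression and are alive or lost to survival follow-up.
5. Add the two analyses of step 7, with the visit interval in (1) fixed in advance. In neither does a distant later death set status. Label them sensitivity analyses, not bounds: both fall below the true median if patients who leave progress more slowly than those who stay.

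The cost is a few lines of SAP text, two further runs of an existing derivation on existing data, and two extra PFS estimates to report and explain.
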